6.5.2.3 Participants will be instructed in the proper methods for performing each exercise by an ACSM Certified Exercise PhysiologistSM. For those randomized to the dyadic intervention, this will involve a 45-60 minute meeting between the Physiologist and both the survivor and the caregiver. For those randomized to the individual intervention, this will involve a 45-60 minute meeting between the Physiologist and the survivor alone.

6.6 ***EXCAP-PA:*** Partner-Assisted Home-Based Walking and Progressive Resistance Exercise Program

6.6.1 Those randomized to Arm 1, the Partner-Assisted version of EXCAP, will receive the EXCAP program instruction as a dyad, as described above. After the Physiologist has demonstrated proper methods for performing each exercise to the dyad, a trained member of the study team will meet with participants. This meeting will involve a discussion of barriers that might reduce adherence to the intervention for each participant, ways that cancer survivor and caregiver can support one another in remaining adherent, and ways of dealing with stress (including LGBT minority stress). Those randomized to Arm 2, survivor-only EXCAP, will not discuss dyadic support or ways of dealing with stress.

6.7 ***Intervention contact and tracking***

6.7.1 A study team member will make phone or e-mail contact with participants each week to answer any questions they may have regarding the exercise program and to facilitate proper adherence

and compliance to the exercise intervention. In Arm 1, the team member will speak with both the cancer survivor and the caregiver together. In Arm 2, the study team member will speak with the cancer survivor alone.

- 6.7.2 Participants will also complete a daily diary throughout the intervention period recording mood/psychological distress (all study participants) and physical activity (those randomized to receive exercise only). (Note: The daily diary will take approximately 30 seconds to complete.)
- 6.7.3 All Walking and Progressive Resistance Exercises will be performed off-site from the University of Rochester Cancer Center in a home-based participant-selected environment.

6.8 *Post-intervention assessment*

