- 6.8.1 Procedures for the post-intervention assessment will follow those from the baseline assessment. First, blood sampling will be done to estimate hematocrit, hemoglobin, t-cells and biological endpoints (e.g., serum amyloid A, CRP, cortisol). Again, a total of approximately 34 ml of blood (around 2 tablespoons) will be drawn, as was done in the baseline assessment.
- 6.8.2 After having blood drawn, all participants will be offered breakfast/a snack in the PEAK Lab. Survivors will then complete survey questionnaires via REDCap first and physical assessments second, while caregivers will complete physical assessments first and questionnaires second.
- 6.8.3 Participants will be evaluated on skeletal muscle mass (bioelectrical impedance), heart rate variability, muscular strength (Handgrip Dynamometry, isokinetic knee flexion/ extension and shoulder diagonal), and aerobic capacity (6 minute walk test).
- 6.8.4 Following completion of all study procedures, dyads will be fully debriefed and given the opportunity to provide final feedback about the intervention in a meeting with the study chair. The two arms of the study will be explained and caregivers randomized to Arm 2 (survivor only EXCAP) will be provided an EXCAP exercise kit and a 45 minute instructional session in the use of the EXCAP exercises with an ACSM Certified Exercise PhysiologistSM.
- 6.8.5 Weekly phone calls or e-mails from a study team member, as detailed above, will desist when the participant's involvement in the study has ended, following the post-intervention assessment.

- 6.9 **Costs/Payments:** There will be no costs to survivors or caregivers for the physiological assessments (e.g. serum collection, bioelectrical impedance, and muscular strength), Resistance bands, Pedometers (or Fitness trackers), Actigraphs or Home-Based Walking and Progressive Resistance Exercise Prescription. All assessments, which are conducted and collected for research purposes only, will be paid for from funds controlled by [name] in the Cancer Control Unit within the James P. Wilmot Cancer Institute. Parking costs will also be covered.

Each participants will be paid up to \$100 for taking part in this study (\$200 total per dyad). Each survivor and caregiver will be paid \$40 for coming to the baseline visit and \$60 for coming to the

second visit. In addition, each participant will receive an exercise kit, including a pedometer and resistance bands, free of charge.

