8. REPORTABLE EVENTS

8.1 *Data and Safety Monitoring*

Clinical Trials Data Safety Monitoring Committee: The Director of the Cancer Center delegates responsibility for continued review and monitoring of all clinical trials conducted by the URCC to the Clinical Trials Data Safety Monitoring Committee. This committee provides oversight of study progress and safety by review of accrual and adverse events at annual meetings. Any adverse event requiring expedited review per protocol will be submitted to the Data Safety Monitoring Committee for determination as to whether further action is required.

The study PI and the study medical monitor determine if the adverse event requires expedited review. Interim meetings are scheduled, as needed, to address specific issues that require immediate attention to assure patient safety.

The Committee:

- a) Reviews assigned clinical trials conducted at the URCC for progress and safety
- b) Reviews all adverse events requiring expedited reporting as defined in the protocol
- c) Reviews reports generated by the URCC data quality control review process
- d) Submits recommendations for corrective actions to the Protocol Review Committee and the PI
- e) In general, outcome data is not made available to individuals outside of the DSMC until accrual has been completed and all participants have completed the intervention. At this time, the DSMC may approve the release of outcome data on a confidential basis to the trial PI for planning the preparation of manuscripts and/or to a small number of other investigators for purposes of planning future trials. Any release of outcome data prior to the DSMC's recommendation for general dissemination of results must be reviewed and approved by the DSMC.

Safety Coordinator: The Medical Director of the Cancer Center Clinical Trials Office appoints the Safety Coordinator. The Safety Coordinator monitors adverse event rates utilizing the URCC Clinical Trials database. If any DSMC assigned study has had two or more of the same SAEs reported in a month or more than six of the same SAEs in six months, the DSMC will review the summary of SAEs, discuss events with the Study Chair, and conduct a more detailed review with the Study Chair. The Data Safety Monitoring Chair will determine if further action is required.

The Safety Coordinator:

- a) Forwards all adverse events requiring expedited reporting to the Data Safety Monitoring Committee Chair who determines if immediate action is required

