- b) Maintains a database of all adverse events requiring expedited reporting
- c) Insures all reports are available for all meetings of the Data Safety Monitoring Committee

Protocol date: 7/06/2020

- d) Monitors adverse event rates utilizing the URCC Clinical Trials database.

8.2 *Adverse Reporting Requirements:*

- 8.2.1 Adverse reactions to the EXCAP or EXCAP-PA Exercise Programs will be reported to the University of Rochester Medical Center IRB using the University reporting form and University of Rochester Medical Center adverse event reporting procedures.
- 8.2.2 Serious adverse events, while a participant is on study until 14 days after the date the participant goes off study, will be reported in writing to the IRB as per their requirements.
- 8.2.3 A serious adverse event is defined as any event that is fatal, life-threatening, disabling or incapacitating or results in hospitalization, prolongs a hospital stay or is associated with congenital abnormality, new cancer diagnosis or overdose.
- 8.2.4 This study will make use of the Common Terminology Criteria for Adverse Events (CTCAE), recommended by the National Cancer Institute. These criteria use five grades for adverse events. Grade refers to the severity of the AE. The CTCAE displays Grades 1 through 5 with unique clinical descriptions of severity for each AE based on this general guideline:
- 8.2.4.1 Grade 1: Mild; asymptomatic or mild symptoms; clinical or diagnostic observations only; intervention not indicated.
 - 8.2.4.2 Grade 2: Moderate; minimal, local or noninvasive intervention indicated; limiting age-appropriate instrumental activities of daily living (ADL).
 - 8.2.4.3 Grade 3: Severe or medically significant but not immediately life-threatening; hospitalization or prolongation of hospitalization indicated; disabling; limiting self-care ADL.
 - 8.2.4.4 Grade 4: Life-threatening consequences; urgent intervention indicated.
 - 8.2.4.5 Grade 5: Death related to AE.

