9. RISK/BENEFIT ASSESSMENT

- 9.1 ***Risks to participants:*** There are four potential risks associated with participation in the proposed study: 1) physical harm associated with assessment procedures, 2) physical harm associated with intervention procedures, 3) emotional distress and 4) loss of confidentiality.
- 9.1.1 In terms of physical harm associated with assessment procedures, risks associated with a 6-minute walk test are similar to participation in a moderate to vigorous walking exercise program and are minimal for individuals with no cardiopulmonary, orthopedic, or age identified risk factors as determined by a physician. Risks include muscle cramps, muscle strain and/or joint injury, delayed muscle soreness, lightheadedness, and fatigue. Handgrip Dynamometry and Biodex isokinetic tests for strength may cause minor stiffness and/or tenderness in muscles for a couple of days following testing. The nature of these assessments will require a level of exertion; this exertion may cause temporary changes such as an increase in heart rate and blood pressure, both of which are normal responses to vigorous exercise. There is a small risk of irritation to the skin from the electrodes used for the BIA analysis.
- 9.1.2 In terms of physical harm associated with intervention procedures, commencement of a moderate walking and progressive resistance exercise program is not associated with any severe side effects and risks are minimal for individuals with no cardiopulmonary, orthopedic, or age identified risk factors as determined by a physician. The absolute chance of a cardiac event among adults while engaging in vigorous exercise is one per year for every 15,000 to 18,000 people.⁵⁹ A transient increase in blood pressure may occur with all types of exercise. Although unlikely, a moderate walking and progressive resistance exercise program may also cause musculoskeletal effects, such as mild muscle soreness, a muscle strain, or other related accidental injuries such as tripping. Overall, the risk level for participation in the moderate intensity EXCAP Home-Based Walking and Progressive Resistance program is minimal.

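### Non-serious adverse events have no cause-neutral recording rule, and the only scheduled contact between visits reaches caregivers in Arm 1 but not in Arm 2

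*Combined protocol and SAP*

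**What the plan says.** **Reporting rules (section 8.2).** For events that are not serious, the only explicit statement is in 8.2.1: "Adverse reactions to the EXCAP or EXCAP-PA Exercise Programs will be reported to the University of Rochester Medical Center IRB". Section 8.2.2 covers "Serious adverse events, while a participant is on study until 14 days after the date the participant goes off study", with no restriction by arm, role or cause. Severity is graded by CTCAE (8.2.4): "These criteria use five grades for adverse events".

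**Oversight (section 8.1).** Of the monitoring committee the plan says: "This committee provides oversight of study progress and safety by review of accrual and adverse events at annual meetings". The Safety Coordinator "Monitors adverse event rates utilizing the URCC Clinical Trials database". The database that this role maintains is described as holding events that require expedited reporting.

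**Risks (section 9.1).** "There are four potential risks associated with participation in the proposed study": physical harm from assessments, physical harm from the intervention, emotional distress, and loss of confidentiality.

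**Contact between visits (section 6.7.1).** Staff make weekly contact to answer questions about the exercise programme and support adherence. In Arm 1 they speak with survivor and caregiver together. "In Arm 2, the study team member will speak with the cancer survivor alone". The intervention protocols in the Appendix say the same.

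**Other caregiver contact.** Section 6.4.1 applies every assessment to all survivors and caregivers. Section 6.3.3 returns the actigraph to everyone before the second visit. Section 6.8.4 has all dyads debriefed, after which "caregivers randomized to Arm 2 (survivor only EXCAP) will be provided an EXCAP exercise kit and a 45 minute instructional session".

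**Forms and analysis.** Table 11.1 has no adverse-event form. Section 13 has no safety analysis.

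**The concern.** Caregivers in both arms undergo the same blood draws, questionnaires and strength and walk tests. Section 9.1.1 expects minor harms from the tests, including soreness that may last a couple of days and so may appear after the participant has gone home. Section 9.1.3 expects that questionnaires or the intervention may cause distress or tension within the dyad. None of these is a reaction to the exercise programme, so none falls under the only explicit rule for non-serious events.

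The opportunity to mention such an event also depends on arm. An Arm 1 caregiver can raise it on the next weekly call, and an Arm 2 caregiver has no such call. Arm 2 caregivers receive no programme during the study period (section 6.4.7), so in that period a non-serious caregiver event can meet 8.2.1 only in Arm 1.

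At stake is any statement about caregiver safety by arm. Section 2.5.1 already compares caregivers by arm on distress and biological endpoints. Section 13.3.1 says the trial will inform a Phase III trial, and section 1.2 cites earlier EXCAP work as free of adverse events. A similar statement from this trial could not be separated from the way events were collected.

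**Working it through.** The plan gives no event rate or safety figure, so there is nothing to reproduce. The check consists of two counts and a comparison of sections.

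**1. Risks covered by the non-serious rule**

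| Risk in 9.1 | Named in 8.2.1 | Other provision |
|---|---|---|
| Harm from assessments | No | Supervised testing (9.2.1) |
| Harm from the intervention | Yes | Physiologist available by phone or e-mail (9.2.1) |
| Emotional distress | No | Notification, triage and referral (9.2.2); PHQ-9 referral (10.1.2) |
| Loss of confidentiality | No | Data-security steps (9.2.3) |

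The rule covers 1 of 4 risks and leaves 4 - 1 = 3 without an explicit recording rule when the event is non-serious. The provisions in the last column prevent or manage a problem. None is stated to create an event record. Any of the four that meets the definition in 8.2.3 is reportable in both arms under 8.2.2.

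**2. Scheduled weekly caregiver contacts**

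Inputs: 35 dyads per arm (section 5.1), 6 weeks of intervention (sections 4.1 and 5.2), one contact per week (section 6.7.1).

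- Arm 1: 35 x 6 = 210.
- Arm 2: 35 x 0 = 0.

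This assumes that every contact is made and every dyad stays in. It counts weekly contacts only. Both arms also have 2 assessment visits per caregiver, plus the debrief.

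**3. Effect on recorded counts**

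Let q be the true risk of a non-serious event in a caregiver, equal in both arms, and let c1 and c2 be the probabilities that such an event is recorded in Arms 1 and 2. The expected difference in recorded events is 35 x q x (c1 - c2).

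- If c1 = c2 it is zero, whatever q is.
- If c1 > c2, as the weekly calls make likely, Arm 1 shows an excess with no true difference.
- Arm 2 shows an expected count of zero only if q = 0 or c2 = 0, and the documents do not establish either.

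The documents give no value for q, c1 or c2. The direction can be argued, but the size cannot be computed.

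**4. The daily diary**

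Section 6.7.2 and the diary paragraph in section 10.2.1 have all participants rate daily distress. Table 11.1 limits the diary to those exercising. This decides whether Arm 2 caregivers have any regular reporting route between visits. Even on the wider reading, their diary holds one 0-10 distress item and nothing on physical events.

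**The case against.** The strongest reply is that 8.2.1 says what goes to the IRB, not what is recorded. It does not use the word only, and it refers to a University form and procedures that are not in these documents and may be wider. The committee reviews adverse events without limiting them to exercise reactions, and CTCAE grading reaches down to mild events. Table 11.1 lists measures by visit, so a form completed when an event occurs need not appear there. Caregiver data are for exploratory use (section 4.1), and no by-arm safety comparison is planned.

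Much of this stands, and it rules out three stronger readings that a reader might infer:

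- *That Arm 2 caregivers are out of contact for the whole intervention.* They attend both visits and the debrief, get the actigraph back before the second visit and, on one reading, keep the diary. Only the weekly contact is missing.
- *That caregiver harm can show only in Arm 1.* That holds for non-serious reactions under 8.2.1 during the study period. Serious events count in both arms, and POMS, PHQ-9 and STAI are completed by all caregivers at both visits.
- *That three of the four risks go uncounted.* The documents show that no recording rule is stated, not that nothing is recorded.

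What the reply does not meet is collection. Reviewing, grading and monitoring rates act on events that someone has already elicited. The documents do not say who asks about non-serious events, when, or with what question, and the only scheduled contact between visits differs by arm for caregivers. Harm apparent during a supervised test is observed equally; harm that appears at home is not.

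**Conclusion.** The concern holds in a limited form. One of the four named risks has an explicit rule for non-serious events and three do not. Scheduled weekly caregiver contacts are 210 in Arm 1 and 0 in Arm 2, so non-serious caregiver events are ascertained unequally. A by-arm caregiver safety statement would probably be biased against EXCAP-PA, because its caregivers have more occasions to report.

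This rests on two assumptions: that some events are mentioned on weekly calls although the calls are not designed to ask about them, and that no unseen institutional procedure elicits events equally in both arms. The imbalance concerns caregivers; survivors have weekly contact in both arms. Serious events and the primary analysis are not affected.

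A reader might also infer that the 14-day serious-event window is too short for Arm 2 caregivers, who receive a kit on leaving. The documents describe no monitored course after exit, and that period has no bearing on the comparison between arms.

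**What to change.** 1. **Reword 8.2.1** so that all adverse events from consent onward are recorded whatever the suspected cause, with relatedness noted. Apply CTCAE grading to clinical events and log confidentiality breaches separately, since a severity grade does not suit them.
2. **Ask one identical adverse-event question** of every survivor and caregiver in both arms at the existing post-intervention visit, covering the whole period since baseline. Add it to table 11.1.
3. **Base any by-arm caregiver safety summary on that question alone**, with the number asked in each arm as the denominator. List events volunteered on weekly calls separately.
4. **Reconcile the diary scope** in sections 6.7.2 and 10.2.1 (all participants) with table 11.1 (those exercising).

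The cost is amendment wording, one short item at a visit that already takes place, and one added line in the table. More minor events will be recorded. Recall over six weeks may miss some, and Arm 1 caregivers who discussed an event on a call may remember it better, so most of the imbalance goes but perhaps not all. Caregivers who miss the second visit will not be asked; the plan expects 60 of 70 to attend. Adding weekly contact for Arm 2 caregivers is not advised: the design deliberately leaves them unengaged, and regular messages would change the comparator.

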In **discussing LGBT specific stress**, the interventionist asks the LGBT cancer survivor open ended questions about experiences as a sexual minority individual seeking cancer care. The LGBT survivor will guide the discussion, but the interventionist may ask about how being a sexual minority affected relationships with care providers, unmet needs that arose during care, and how identity shapes experience of survivorship. The caregiver will then be asked to contribute any of their experiences in providing care for the LGBT survivor. Exercise is introduced in this context as a way the dyad can support one another, even in the stress of cancer or the stress of being a sexual minority seeking cancer care.

In **assessing barriers**, the interventionist asks both participants about the barriers that might interfere with their ability to exercise over the next week. Barriers could include daily obligations, physical concerns or symptoms, or emotional or motivational concerns. Both LGBT survivor and caregiver share their anticipated barriers with one another and with the interventionist.

In behavioral activation research, assessing barriers to accomplishing a behavioral goal is a well-validated method of ensuring goal completion.^{93,94} The same technique is used in Motivational Interviewing, to elicit "change talk" and increase motivation to engage in the behavioral change.⁹⁵⁻⁹⁷

In **eliciting supportive behaviors**, the interventionist first turns the focus onto the LGBT cancer survivor, asking what behaviors by the caregiver would help to overcome the aforementioned barriers. Gentle Socratic questioning is used to refine the exact form of and rationale for these behaviors.

The interventionist then checks in with the caregiver, asking what behaviors the caregiver will try over this next week in supporting the LGBT survivor in overcoming barriers to exercise. Again, questioning is used to ensure that the caregiver knows exactly what behaviors would be most helpful. A final check with the LGBT survivor sets the collaborative goal and expectation for the week.

Supportive behavior exchange is a common technique in many dyadic interventions.⁹⁸⁻¹⁰⁰ Typically behavior exchange techniques involve eliciting desired behaviors from each member

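### SAEs are reportable until 14 days after a participant goes off study, but routine contact ends at the post-intervention visit and no planned contact, diary item or form carries a scripted adverse event question

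*Combined protocol and SAP*

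**What the plan says.** **The obligation.** Section 8.2.2 makes reportable "Serious adverse events, while a participant is on study until 14 days after the date the participant goes off study". Section 8.2.3 defines a serious event broadly. It includes any hospitalization and any new cancer diagnosis, whatever the cause. Sections 8.1 and 8.2 then describe review, grading and onward reporting. They do not say how staff learn of an event, and they do not define the off-study date.

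**The contacts.** Section 6.7.1 has a team member contact participants "each week to answer any questions they may have regarding the exercise program and to facilitate proper adherence" and compliance. It adds: "In Arm 2, the study team member will speak with the cancer survivor alone". The Appendix confirms that Arm 2 calls go to the survivor only. In the Appendix's account of the dyadic (EXCAP-PA) framework, which the Arm 1 calls follow, the closest thing to a symptom question is the talk about obstacles to exercising: "Barriers could include daily obligations, physical concerns or symptoms, or emotional or motivational concerns".

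**The records.** The daily diary (6.7.2 and 10.2.1.2) covers distress, steps, resistance minutes and perceived exertion. The 11.1 table lists no adverse event or hospitalization form, and its medication and clinical record forms are for baseline only.

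**The end of contact.** At the last visit dyads are "given the opportunity to provide final feedback about the intervention in a meeting with the study chair" (6.8.4). Section 6.8.5 then states: "Weekly phone calls or e-mails from a study team member, as detailed above, will desist when the" participant's involvement ends after that assessment.

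**The concern.** One stated rule ends contact inside a period that another stated rule requires to be covered. A team that follows the plan exactly stops calling and e-mailing at about the moment the 14-day tail begins. It has not been told to ask about serious events before then either.

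The tail is not an empty period. The post-intervention visit repeats the fitness tests (6.8.3), and 10.2.2 describes the walk test as maximal. Section 9.1.1 expects some muscle effects to last a couple of days after strength testing. It is also the visit at which "caregivers randomized to Arm 2 (survivor only EXCAP) will be provided an EXCAP exercise kit" and instruction in its use.

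At stake is whether a hospitalization at home, or in the two weeks after the last visit, reaches the IRB and the data safety monitoring committee. The Safety Coordinator's trigger in 8.1 counts reported SAEs, so it works only as well as events are captured. A low SAE count collected without asking would be weak reassurance.

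**Working it through.** The plan gives no figure to reproduce here. The check is a comparison of sections, followed by simple arithmetic for the size of the uncovered period.

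**1. Is there a scripted question anywhere in the routine schedule?**

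| Planned contact or record | Stated content | Scripted adverse event question? |
|---|---|---|
| Weekly call or e-mail (6.7.1; Appendix) | Exercise questions, progress, barriers, adherence, goals; not made to Arm 2 caregivers | No |
| Daily diary (6.7.2, 10.2.1.2) | Distress for all; activity for exercisers | No |
| Forms (11.1) | Questionnaires, fitness tests, blood, activity monitoring | No |
| Post-intervention debriefing (6.8.4) | Feedback on the intervention | No, though an attender could mention an event |
| After the last visit (6.8.5) | Nothing routine | No contact |

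Later contact is conditional only. There is a check-in call for someone distressed at an assessment and already in care (9.2.2), and brochure follow-up for those who agreed to pass on study information (4.2.1). Staff can open clinical records, but the stated use is to complete enrollment forms (4.4.3, 6.3.2).

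**2. How long is the uncovered tail?**

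Inputs: intervention of 42 days (4.1); tail of 14 days (8.2.2); 140 individuals (3.1). Assumption: the off-study date is the post-intervention visit, at about day 42.

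- Window after baseline: 42 + 14 = 56 days per person; 140 × 56 = 7,840 person-days.
- Tail: 140 × 14 = 1,960 person-days.
- Share: 1,960 / 7,840 = 14 / 56 = 25%.

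**3. Does attrition change this?**

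Sections 4.1 and 13.4.1 plan for 120 of 140 individuals to remain, so 20 leave. Suppose all 20 leave on day d, and each has a 14-day tail from that day.

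- Total person-days = 120 × 56 + 20 × (d + 14); tail = 140 × 14 = 1,960.
- d = 0: 1,960 / 7,000 = 28.0%.
- d = 21: 1,960 / 7,420 = 26.4%.
- d = 41: 1,960 / 7,820 = 25.1%.

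The share is therefore 25% to 28% over the whole range of leaving times. The leavers also lose the debriefing, which is the one in-person opportunity to mention an earlier event. Section 13.4.1 names illness among the expected reasons for attrition.

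**The case against.** The strongest reply is that this argues from silence. Section 8.2.2 is a reporting rule, and how events are elicited is often set elsewhere. Section 8.2.1 defers to University adverse event procedures that are not in the documents, and the consent pages were removed from the text available here. Informal routes also exist. Section 4.1 says each participant will be monitored by a certified exercise physiologist. The Appendix has standard weekly calls check progress and troubleshoot barriers. Section 9.2.1 tells participants to stop if they have cardiopulmonary symptoms, and makes a physiologist reachable by phone or e-mail. A survivor admitted to hospital during a daily walking program would probably come to light in the next progress call. Section 9.1.2 describes program risk as minimal.

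Much of this stands. It means that events during the 6 weeks are not simply unseen. It does not supply a scripted question, and it does not reach past the last visit except when the participant makes contact. Consent wording that asks people to report problems would rely on the participant in the same way.

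A reader might go further in three ways that the documents do not support.

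- *Adding the Arm 2 caregivers' intervention days to the tail.* This gives 35 × 42 + 1,960 = 3,430 of 7,840 person-days, or 44%. It is not a measure of missed capture. These caregivers are told not to change their exercise, their partner is called weekly, and those who complete can report earlier events at the last visit.
- *Treating the Arm 2 caregivers' 14 days after receiving the kit as program exposure.* Being given a kit does not show that anyone exercised on those days.
- *Concluding that a comparison of caregiver SAEs by arm is compromised.* Sections 13.1 to 13.3 plan no such comparison, and 4.1 makes caregiver data exploratory.

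**Conclusion.** The point holds as a modest gap in safety procedures, worth a cheap improvement. The plan requires SAE reporting through a 14-day tail in which it schedules no routine contact for anyone. Its earlier contacts carry no scripted adverse event question, and Arm 2 caregivers have no weekly contact. The tail is 25% of the 56 days after baseline, or 25% to 28% with the planned attrition.

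These shares assume that off study means the post-intervention visit or withdrawal. An earlier off-study date would place part of the tail before the last visit, and a later one would lengthen the period without contact. The percentage measures time without planned contact and does not estimate missed events. No event risk is assumed, and nothing in the documents shows that an SAE was or would be missed. The primary efficacy analysis is unaffected.

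**What to change.** Make three changes.

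1. In 8.2, define the off-study date as the date of the post-intervention visit or of withdrawal.
2. Add one scripted phone or e-mail check 14 days after that date, for all survivors and caregivers in both arms unless contact is declined. It should ask about any hospitalization or other serious event since baseline.
3. Ask the same question in the existing weekly contacts and at the post-intervention visit.

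Do not add weekly calls to Arm 2 caregivers, because that would change their condition. The day-14 check looks back to baseline and is the same in both arms, so it also covers their intervention period. The committee, the Safety Coordinator and the SAE count rule in 8.1 can stay as they are.

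The cost is at most 140 short contacts by existing staff, one extra question in about 70 × 6 = 420 weekly contacts already planned, and a few sentences of text. Some minor or unrelated events will be reported and need sorting. Not everyone will answer the closing check, so capture will improve but will not be complete.
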